**Hyperpolarized Xenon gas MR Imaging in Radiotherapy**

possible through collection of gas and dissolved-phase signal within a single acquisition of images.

Initially Albert *et al* demonstrated imaging of the lung airspaces using hyperpolarized Xe-129 introduced into the trachea of a mouse heart-lung model (14). High signal intensity was achieved using 25ml (3atm) of Xe-129 polarized to approximately 25%. This was followed by a combined imaging and spectroscopic approach by Mugler *et al*. Comparison was made between hyperpolarized Xe-129 and conventional H MR images in two human volunteers following inhalation of hyperpolarized Xe-129, polarized to 2%. Significant correlation was shown between the gas space signal absence in conventional MRI and the gas space signal in hyperpolarized Xe-129 images (62).

The dynamics of Xe-129 within the chest have been further studied in a dog (17). This study demonstrated a decay of the Xe-129 MR signal within the gas-phase. This was observed to provide a measure of Xe-129 absorption into the tissue. Time constants for saturation were determined as 61ms and 70ms for tissue and red blood cells respectively.

[figure not shown]
Hyperpolarized Xe-129 MR imaging may be applied as a non-invasive measure of lung function parameters specific to emphysema. The alveolar surface area per unit volume of gas (S/V) represents a primary measure of emphysema that may be evaluated using the chemical shift saturation recovery method (18, 59, 65). Another strategy using hyperpolarized Xe-129 MR is the xenon transfer contrast (XTC) method that may be adapted to derive values of S/V (18, 65). In addition, the XTC method has been used successfully to measure lung septal thickness in animals (63, 68) and humans (65) and evaluate the severity and progression of emphysema (47).

ADC values may also be determined with hyperpolarized Xe-129 MR imaging. However, Xe-129 has a much lower diffusivity than He-3 and demonstrates a lower diffusion coefficient. This offers an advantage over He-3 since measurement of alveolar and small airways dimensions is possible by applying diffusion weighted imaging (65, 69).

[figure not shown]
Hyperpolarized Xe-129 is also susceptible to the paramagnetic effect of oxygen within the pulmonary airspaces. The resultant loss of polarization and predicted decay in MR signal may be used to measure intrapulmonary PO2. However, this is slightly more complex than when measuring with He-3 because additional signal loss due to diffusion of Xe-129 into alveolar tissue needs to be taken into account (18). An equivalent PO2 is determined accounting for signal decay due to the presence of oxygen and Xe-129 diffusion.

At our Oxford centre, we have already commenced studies using hyperpolarized Xe-129 MR imaging in normal healthy volunteers and patients with chronic obstructive pulmonary disease (COPD). To date, we have administered 51 doses of 1L hyperpolarized xenon gas to 16 study participants for completion of hyperpolarized Xe-129 MR imaging. These have all been well tolerated with no serious adverse events. Preliminary results have shown that hyperpolarized Xe-129 MRI is a viable functional lung imaging modality. Images acquired from a normal healthy volunteer and patient with COPD using our scanner are shown below in *Figures 2, 3*.

[figure not shown]
### HEALTHY VOLUNTEER

A) Conventional MRI

[figure not shown]
B) Xe-129 MRI

[figure not shown]
C) Computed Tomography (CT) in lung windows

(Figure 2) Coronal images acquired from a healthy volunteer. A) Conventional MRI demonstrates no signal from the lung. B) Xe-129 MRI shows homogeneous ventilation signal throughout the lung. C) CT shows detailed lung structure.

[figure not shown]
### COPD

A) Conventional MRI

[figure not shown]

B) Xe-129 MRI

C) CT in lung windows

(Figure 3a) Coronal images acquired from a patient with COPD. A) Conventional MRI demonstrates no signal from the lung. B) Xe-129 MRI shows abnormal heterogeneous ventilation signal throughout the lung. C) CT shows severe paraseptal emphysema.

**COPD**

A) Xe-129 MRI

B) Xe-129 MRI and  
Conventional MRIC) Xe-129 MRI, conventional  
MRI and volumetric CT

*(Figure 3b) Post data processing of coronal images acquired from the same patient with COPD. A) Abstracted Xe-129 MRI ventilation image. B) Abstracted Xe-129 MRI mapped onto conventional MRI. C) Abstracted Xe-129 MRI mapped onto conventional MRI and then volumetric CT data to produce a 3-D image of the lungs.*

## 5. PROPOSED RESEARCH

We aim to use hyperpolarized xenon gas (Xe-129) magnetic resonance imaging (MRI) and computed tomography (CT) imaging as a new technique capable of objectively and quantitatively, describing regional and structural lung abnormality in patients that will be undergoing radiotherapy affecting the lung. We will correlate this technique with baseline physiological and functional measures to determine if respiratory tolerance for radiotherapy is better predicted by hyperpolarized Xe-129 MR imaging. We will also evaluate changes in hyperpolarized-Xe-129 MR imaging before, during and after radiotherapy to determine if it provides improved assessment of radiation-induced lung injury.

MR imaging has an enhanced speed of image acquisition compared with CT and lung scintigraphy and offers the potential of ultra-fast sequences allowing dynamic assessment of lungs during respiration. In conventional MRI, the signal originates principally from the protons in water molecules of tissues. Therefore conventional MRI has limited use in respiratory disease because the lung has a very low density of protons, instead being largely composed of air spaces that do not generate MR signal. Hyperpolarized noble gases can resolve this problem. Helium (He-3) and Xenon (Xe-129) are unreactive or inert noble gases. The both have a nuclear spin of  $\frac{1}{2}$  enabling use in MR imaging to generate a signal.

The study will focus on hyperpolarized Xe-129 MR imaging as xenon is available in unlimited

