## 6. OBJECTIVES AND OUTCOME MEASURES/ENDPOINTS

|           | Objectives  | Outcome Measures/Endpoints  |
|-----------|---|---|
| Primary   | To demonstrate that hyperpolarized Xe-129 is sensitive to change following pulmonary radiotherapy, and thus may be developed as an objective and quantifiable method of functional lung assessment in patients undergoing radiotherapy that affects the lung  | Change in hyperpolarized Xe-129 MR imaging from baseline to other time points post radiotherapy initiation.   |
| Secondary | 
To obtain preliminary data demonstrating if changes in hyperpolarized Xe-129 MR imaging correlate with subjective and objective responses following pulmonary radiotherapy.
 
To obtain preliminary data demonstrating if baseline hyperpolarized Xe-129 MR imaging is a more reliable clinical
 | 
Change in hyperpolarized Xe-129 MR imaging parameters from baseline to other time points post radiotherapy initiation compared to subjective and objective measures of lung function.
 
Comparison of hyperpolarized Xe-129 MR imaging and four-dimensional CT (4D-CT) at baseline.
 |

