**Hyperpolarized Xenon gas MR Imaging in Radiotherapy**

|  |   |   |
|--|---|---|
|  | 
indicator of patient respiratory tolerance to pulmonary radiotherapy than conventional lung function testing by determining the relationship between hyperpolarized Xe-129 MR imaging indices and functional patient outcome measures (dyspnoea and radiation-induced lung toxicity assessment).
 
To use functional lung information in virtual predictive and adaptive radiotherapy treatment planning.
 | 
Retrospective comparison of modified radiotherapy treatment planning incorporating functional lung information from hyperpolarized Xe-129 MR imaging with conventional radiotherapy treatment plans.
 |
|--|---|---|

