### **8.3. Exclusion Criteria**

The participant may not enter the trial if ANY of the following apply:

- Inability to give written informed consent.
- Female participant who is pregnant, lactating or planning pregnancy during the course of the trial.
- Previous radiotherapy to the chest.
- The presence of another condition where the disease itself or treatment may interfere with the study endpoints.
- Any psychological, familial, sociological or geographical condition potentially hampering compliance with the study protocol and follow-up schedule.
- Inability to lie flat for imaging.
- Contraindications to MRI examination including indwelling pacemaker, non-MRI compatible metallic implant, severe claustrophobia, intra-ocular foreign body.
- Contraindications for gadolinium enhanced lung MRI scan – known hypersensitivity/allergy to the injection of MultiHance (contains gadobenate dimeglumine and small quantities of benzyl alcohol) that is given as part of this scanning or an adverse reaction to an injection given during previous MRI scanning, severe renal impairment.
- Epilepsy requiring on-going medical treatment, or a seizure within the past year.

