**Dyspnoea**

Dyspnoea (breathlessness) will be measured using the Dyspnoea-12 score (70), a seven-point Likert scale and a visual analogue score.

**Analysis** will be based on the change in score from the baseline over time.

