**Hyperpolarized Xenon gas MR Imaging in Radiotherapy**

12 score (70) and MRC breathlessness score. We will test the hypothesis that Xe-129 lung MRI has a closer correlation with these measures than FEV1 or gas transfer.

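### The objective on predicting tolerance is listed with a baseline 4D-CT comparison, and no stated analysis links baseline Xe-129 MRI to dyspnoea or RILT after radiotherapy

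*Combined protocol and SAP*

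**What the plan says.** The objective (sections 2 and 6) reads "To obtain preliminary data demonstrating if baseline hyperpolarized Xe-129 MR imaging is a more reliable clinical" indicator of tolerance than conventional lung function testing, to be settled "by determining the relationship between hyperpolarized Xe-129 MR imaging indices and functional patient outcome measures (dyspnoea and radiation-induced lung toxicity assessment". The endpoint in the corresponding position of both tables is "Comparison of hyperpolarized Xe-129 MR imaging and four-dimensional CT (4D-CT) at baseline". Section 12.1 lists that same comparison under technique development.

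Three other places describe a relevant analysis:

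- **Section 5:** "We will correlate this technique with baseline physiological and functional measures to determine if respiratory tolerance for radiotherapy is better predicted" by Xe-129 MRI.
- **Section 9.5, analysis of the Xe-129 scans:** a multivariate correlation of global ventilation and ADC with Dyspnoea-12 and RILT.
- **Section 12.1, superiority over standard tools:** a multivariate correlation of global and lobar Xe-129 data with the Dyspnoea-"12 score (70) and MRC breathlessness score", and a test of whether Xe-129 MRI correlates more closely with these than FEV1 or gas transfer does.

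On data collection, section 9.5 states: "Dyspnoea (breathlessness) will be measured using the Dyspnoea-12 score (70), a seven-point Likert scale and a visual analogue score". Dyspnoea and RILT are assessed at baseline, on the last day of radiotherapy and 3 months later in both patient groups (sections 7.1, 9.6, 9.8 and 9.9), and section 9.5 analyses each as change from baseline.

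**The concern.** The objective is predictive: a scan taken before radiotherapy should indicate how the patient fares afterwards, and do so better than spirometry or gas transfer. The endpoint set against it contains no outcome and no rival predictor. The only sentence that says how prediction will be judged uses measures recorded before any radiation. A correlation among baseline measurements shows that breathless patients tend to have abnormal scans. It says nothing about tolerance of a treatment not yet given.

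A team that followed section 5 and the listed endpoint would therefore give a cross-sectional answer to a predictive question. Section 12.1 does not repair this, because it leaves the time point open, drops one of the two outcomes named in the objective, and relies in part on a scale for which there will be no data.

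**Working it through.** **1. Does any statement pair a baseline scan with a later outcome?**

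| Place | Xe-129 quantity | Set against | When | Lung function comparator |
|---|---|---|---|---|
| Objective (sections 2, 6) | Baseline MRI | Dyspnoea, RILT | Not stated | Conventional testing |
| First secondary endpoint | Change in MRI | Subjective and objective measures | After radiotherapy starts | None as rival predictor |
| Second secondary endpoint | Baseline MRI | 4D-CT | Baseline | None |
| Third secondary endpoint | MRI used in replanning | Conventional plans | Retrospective | None |
| Section 5 | MRI | Physiological and functional measures | Baseline | None named |
| Section 9.5 | Global ventilation, ADC | Dyspnoea-12, RILT | Not stated | None |
| Section 12.1 superiority test | Global and lobar data | Dyspnoea-12, MRC | Not stated | FEV1 or gas transfer |

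No row has baseline MRI as predictor and a post-radiotherapy outcome as response. Only section 5 is expressly baseline against baseline. Sections 9.5 and 12.1 are silent on timing.

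**2. Are the data collected?**

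- Dyspnoea-12, Likert, visual analogue and RILT: baseline, last day and 3 months, in all patients. None at the half-way visit, which has only the Xe-129 scan and adverse event review.
- MRC score: not among the scales in section 9.5, and not added in 9.6, 9.8 or 9.9. Planned observations: none.
- FEV1 and gas transfer: lung cancer patients only. Section 7.1 omits full pulmonary function testing for other diagnoses, and the closed baseline list in 9.6 contains no lung function test.

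**3. Which visit informs RILT?** Section 4.1 places pneumonitis at two to seven months after radiotherapy. The last-day assessment precedes that window. The 3-month visit falls inside it, one month (3 − 2) into a five-month span (7 − 2), so it is the more informative visit but sees only the early part.

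**4. How many patients can contribute?** At most 30. One follow-up visit suffices under section 7.1. A participant who attends only the half-way visit has no post-baseline dyspnoea or RILT value. A participant without lung cancer has no lung function comparator. The documents give neither count.

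**5. What could the specified analysis show?** There is no plan figure to reproduce: section 12.2 bases 30 on feasibility and gives no effect size or power. The following is for scale only. The correlations, RILT rates and pair counts are assumptions, with two-sided 0.05 (section 12.3 does not state sidedness).

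- One correlation, 80% power: r = tanh[(1.960 + 0.842)/√(n − 3)]. For n = 30, tanh(2.802/5.196) = 0.49; for n = 20, 0.59; for n = 15, 0.67.
- 95% interval at n = 30, tanh[atanh(r) ± 1.96/√27]: an observed 0.3 gives −0.07 to 0.60; an observed 0.5 gives 0.17 to 0.73.
- Closer correlation than FEV1, Williams' test for two dependent correlations, 20,000 simulated trials per setting:

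| r with Xe-129 / with FEV1 / between the two | n = 30 | n = 20 | n = 15 |
|---|---|---|---|
| 0.6 / 0.4 / 0.5 | 24% | 17% | 13% |
| 0.6 / 0.3 / 0.5 | 46% | 32% | 24% |
| 0.6 / 0.3 / 0.7 | 70% | 49% | 38% |

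- Expected RILT cases at assumed rates of 10%, 20% and 30%: 3, 6 and 9 among 30 patients; 2, 4 and 6 among 20.

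**The case against.** A reader might infer that the trial cannot show prediction, or that the whole plan is confined to baseline correlations. The documents do not support this. The objective itself names dyspnoea and RILT. Both are recorded after radiotherapy and analysed as change from baseline. Sections 9.8 and 9.9 carry the methods of sections 9 and 12 to the follow-up visits, so the position of the section 9.5 correlation under baseline assessments does not restrict it to baseline. The baseline-only reading rests on one sentence in section 5.

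A reader might also argue that, because "Previous radiotherapy to the chest" is an exclusion, RILT caused by radiotherapy has no variance at baseline. That follows by definition and measures no defect: no passage proposes to analyse baseline RILT alone. If anything, it suggests that post-radiotherapy values were intended.

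Three further points are fair. The objective seeks only preliminary data. Section 12.1 speaks of closer correlation, not prediction. Objectives and endpoints share table cells, so they are paired by paragraph order. The first excuses low power, but not an endpoint that omits the question. The second leaves the predictive objective without an analysis. The third does not matter, because no secondary endpoint in any position links baseline MRI to a later outcome. The third objective's endpoint also lacks a post-radiotherapy outcome, but that objective concerns virtual planning and does not need one.

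**Conclusion.** The point stands as a mismatch and a gap in specification, not as a design that rules out prediction. One of three secondary objectives has an endpoint that does not address it. Section 5 ties prediction to pre-treatment measures. No stated analysis relates baseline MRI to later dyspnoea or RILT. Of the two dyspnoea scales in the section 12.1 test, one (MRC) has no planned data, and RILT is absent from that test. These conclusions come from the text and need no assumed value.

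The calculations depend on assumed correlations, RILT rates and pair counts. Across the settings shown, power to find Xe-129 MRI more closely correlated than FEV1 runs from 13% to 70%, and even 30 pairs leave wide intervals. This is a reason to report estimates and not a superiority verdict. The point should be corrected before analysis.

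**What to change.** - **Sections 2 and 6:** give this objective its own endpoint, the association of a named baseline Xe-129 index with change in Dyspnoea-12 and with CTCAE RILT grade at Visits 4 and 5. Treat 3 months as the more informative time point for RILT.
- **Comparator:** set this beside the same association for baseline FEV1 and gas transfer, in the same patients, limited to those with lung cancer.
- **4D-CT:** keep the comparison under technique development, where section 12.1 already has it.
- **Section 5:** for the prediction claim, refer to post-radiotherapy outcomes instead of baseline measures.
- **Section 12.1:** state the time points and baseline MRI as predictor, add RILT, and replace the MRC score with the Likert or visual analogue score already collected.
- **Reporting:** state the evaluable number for each analysis and present preliminary estimates with confidence intervals.

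The cost is wording in sections 2, 5, 6 and 12.1. No new procedure is needed so long as MRC is dropped and the head-to-head comparison stays within lung cancer patients; extending it to other diagnoses would require new lung function tests. The downside is a smaller sample: the evaluable number falls below 30 if any participant attends only the half-way visit and, for the head-to-head comparison, if any has a diagnosis other than lung cancer.

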### Hyperpolarized Xenon gas MR Imaging in Radiotherapy

supply in nature and has certain advantageous properties over He-3 including increased lipid solubility. Xe-129 is hyperpolarized, that is to say that nuclear spin within the atoms is increased. Hyperpolarization increases the MR signal enabling the Xe-129 gas to show up on the MR scan. In portions of the lung that have good airflow, the hyperpolarized Xe-129 gas will show up more and be seen more quickly. In addition Xe-129 readily dissolves in blood where it emits different MR signal characteristics. This property may be exploited to regionally quantify both ventilation and perfusion within the lung providing a comprehensive assessment of lung function.

The need for improved functional imaging to identify pre-existing lung disease and predict respiratory tolerance of patients undergoing radiotherapy affecting the lung is clear. Hyperpolarized Xe-129 MR imaging has the potential to inform individual suitability for radiotherapy schedules better than the investigations used currently. In addition improved functional imaging is required to monitor treatment response and enable treatment regimes to be tailored to the individual. Hyperpolarized Xe-129 MR imaging offers the potential of improved detection of radiation-induced lung injury, invaluable to treating patients with radiation induced injury. It may also provide information that would allow RT to be planned in such a way as to reduce the risk of patients developing RLIT.

## 6. OBJECTIVES AND OUTCOME MEASURES/ENDPOINTS

|           | Objectives  | Outcome Measures/Endpoints  |
|-----------|---|---|
| Primary   | To demonstrate that hyperpolarized Xe-129 is sensitive to change following pulmonary radiotherapy, and thus may be developed as an objective and quantifiable method of functional lung assessment in patients undergoing radiotherapy that affects the lung  | Change in hyperpolarized Xe-129 MR imaging from baseline to other time points post radiotherapy initiation.   |
| Secondary | 
To obtain preliminary data demonstrating if changes in hyperpolarized Xe-129 MR imaging correlate with subjective and objective responses following pulmonary radiotherapy.
 
To obtain preliminary data demonstrating if baseline hyperpolarized Xe-129 MR imaging is a more reliable clinical
 | 
Change in hyperpolarized Xe-129 MR imaging parameters from baseline to other time points post radiotherapy initiation compared to subjective and objective measures of lung function.
 
Comparison of hyperpolarized Xe-129 MR imaging and four-dimensional CT (4D-CT) at baseline.
 |

**Hyperpolarized Xenon gas MR Imaging in Radiotherapy**

|  |   |   |
|--|---|---|
|  | 
indicator of patient respiratory tolerance to pulmonary radiotherapy than conventional lung function testing by determining the relationship between hyperpolarized Xe-129 MR imaging indices and functional patient outcome measures (dyspnoea and radiation-induced lung toxicity assessment).
 
To use functional lung information in virtual predictive and adaptive radiotherapy treatment planning.
 | 
Retrospective comparison of modified radiotherapy treatment planning incorporating functional lung information from hyperpolarized Xe-129 MR imaging with conventional radiotherapy treatment plans.
 |
|--|---|---|

## 7. TRIAL DESIGN

### 7.1. Summary of Study Design

This will be an open, single-centred study in the UK. The study group will include 30 patients who are considered suitable for radiotherapy that will affect the lung. Participants considered for radiotherapy that will affect the lung include those with a diagnosis of lung cancer and those with other diagnoses, for example, oesophageal cancer, chest wall tumours and lymphoma. All potential participants for this study undergo an *enrolment visit* (Visit 1). This is an opportunity to discuss the study in more detail, and for those choosing to take part to gain informed, written consent. Eligibility criteria will be checked. All female participants of child-bearing age will have had pregnancy excluded as part of their routine clinical care in Oncology prior to starting radiotherapy. Volunteers will be invited to undertake a 'dummy run' of Xe-129 lung MRI imaging, during which they lie on a couch similar to that used during the MRI, and practice the manoeuvre required when breathing in xenon from a 1L bag during subsequent lung imaging. During the dummy run this will simply be air or oxygen in the 1L bag.

The enrolment and baseline visits are compulsory for all participants. Participants will be required to complete at least one follow-up visit from the "half-way through" following commencement of radiotherapy, end of treatment and 3-months post-radiotherapy visits. The three follow-up visits will be offered to all patients, however completion of only one visit post-commencement of radiotherapy will be compulsory.

At the first baseline imaging visit (Visit 2), patients will be offered hyperpolarized xenon MR imaging, gadolinium-enhanced lung MRI and ventilation/perfusion nuclear medicine scan of the chest (optional) in addition to routine thoracic CT imaging. This enables co-registration between imaging modalities and correlation with physiological variables. Hyperpolarized xenon MR imaging involves acquisition of up to four MR sequences during one scanning session i.e. the participant will undergo up to four hyperpolarized xenon breath holds during each visit. The four inhalations may be different sequences or the same sequence may be repeated to assess reproducibility. Previous studies have shown that the signal from each xenon breath hold clears within seconds of exhalation. Participants will receive radiotherapy schedules according to departmental protocols. Patients will be offered hyperpolarized xenon MRI half-way through their radiotherapy schedule (Visit 3). At this time point no other imaging tests will be completed. In addition to routine thoracic CT, further hyperpolarized Xe-129 MRI and gadolinium-enhanced lung MRI will be offered on the final day of treatment and 3 months following completion of radiotherapy (Visits 4 & 5).

During each visit, patients are scheduled to undergo up to four hyperpolarized Xe-129 breath holds to complete MRI scanning. In the event that breathing and scanning are not entirely synchronised, one or two xenon breath holds may need to be repeated; so in total, each participant will undergo up to a maximum of 24 hyperpolarized Xe-129 breath holds during the four imaging visits over the 9 month study period.

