## **9. TRIAL PROCEDURES**

### **9.1. Recruitment**

**Hyperpolarized Xenon gas MR Imaging in Radiotherapy**

Potential participants will be identified from out-patient Lung cancer or Oncology clinic appointments. Potential participants will be approached by a member of their clinical team within the hospital setting. Any potential participant fulfilling the inclusion criteria will be informed of the trial by a member of their clinical team. If a patient expresses an interest in the study, they will be given a patient information leaflet and will be asked to give their permission to be contacted by the study team. The leaflet will also provide contact details for the study team should the patient wish to initiate contact.

A member of the study team will contact the participant to arrange an enrolment visit (Visit 1). This may be arranged to coincide with a scheduled out-patient clinic appointment for convenience. Enrolment will involve checking that the patient is eligible for the study, completion of informed consent and study registration. This will be an opportunity to discuss the study in detail, familiarise the participant with the Radiology department where the majority of study measures will take place and to complete a “dummy run” of Xe-129 lung MR imaging as previously described in section 7.1.

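### The only stated pregnancy check has to be done before radiotherapy, which does not by itself guarantee that it is done before the first xenon MRI at Visit 2

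*Combined protocol and SAP*

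**What the plan says.** Section 8.3 opens its list of exclusions with "The participant may not enter the trial if ANY of the following apply", and the list includes "Female participant who is pregnant, lactating or planning pregnancy during the course of the trial".

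Eligibility is assessed at enrolment (Visit 1). Section 7.1 says of that visit "Eligibility criteria will be checked", and section 9.1 says "Enrolment will involve checking that the patient is eligible for the study, completion of informed consent and study registration".

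On how pregnancy is ruled out, section 7.1 says "All female participants of child-bearing age will have had pregnancy excluded as part of their routine clinical care in Oncology prior to starting radiotherapy". Section 9.3 (screening and eligibility) and section 10.1 (description of the investigational product) repeat the sentence. No readable section lists a pregnancy test among the Visit 1 or Visit 2 procedures, or asks the study team to obtain the Oncology result before giving xenon.

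On the visits, section 7.1 says "The enrolment and baseline visits are compulsory for all participants". Xenon MRI is first offered at the baseline visit, Visit 2.

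**The concern.** A criterion that bars entry should be settled before a participant receives anything investigational. Here the criterion is tied to Visit 1, but the one stated means of verifying it is tied to a different event, the start of radiotherapy. Visit 2 lies between the two.

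What is at stake is participant safety. Section 11.1 asks for any pregnancy during the trial to be recorded and its outcome followed up, so the plan itself treats pregnancy as important. Visit 2 also involves more than xenon. Patients with lung cancer are offered gadolinium-enhanced MRI and an optional nuclear medicine ventilation/perfusion scan, and section 16.7 says these are additional to routine scans. An undetected pregnancy would therefore matter for the whole Visit 2 session.

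**Working it through.** No arithmetic applies, because the question is one of order. The check compares the deadline with the visit sequence.

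**Step 1. Does Visit 2 come before radiotherapy?** Yes, on three grounds.
- Section 5 states "We will also evaluate changes in hyperpolarized-Xe-129 MR imaging before, during and after radiotherapy", so one imaging time point must precede treatment, and Visit 2 is the only candidate: Visit 3 is half-way through the radiotherapy schedule, Visit 4 is its last day, and Visit 5 is three months after it ends.
- Section 9.7 keeps the treating oncologist blind to the baseline xenon images during radiotherapy planning, which treats Visit 2 as coming before treatment.
- The primary endpoint in section 6 is change from baseline to time points after radiotherapy has begun.

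**Step 2. What does the deadline guarantee at each visit?**

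| Visit | Study imaging | Position | Check guaranteed beforehand by the stated deadline? |
|---|---|---|---|
| 1, enrolment | none (practice run with air or oxygen) | before radiotherapy | no |
| 2, baseline | xenon MRI; for lung cancer also gadolinium MRI and an optional nuclear medicine scan | before radiotherapy | no |
| 3, half-way | xenon MRI | during radiotherapy | yes |
| 4, final day | xenon MRI; for lung cancer also gadolinium MRI | last day of radiotherapy | yes |
| 5, three months | xenon MRI; for lung cancer also gadolinium MRI | after radiotherapy | yes |

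A check done between Visit 2 and the first radiotherapy fraction satisfies the sentence as written. The deadline therefore covers three of the four imaging visits. The one it leaves open is the visit with the first investigational dose.

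**Step 3. Does the position of the sentence supply the missing limit?** Not conclusively. In section 7.1 it follows the Visit 1 eligibility statement, which favours an early check. In section 9.3 it sits under an assessment spread over one or two hospital visits that includes the baseline measures of section 9.5, and those include the xenon MRI. In section 10.1, where a limit tied to dosing would be expected, the deadline is still radiotherapy.

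**Step 4. Does the plan set a limit of the needed kind elsewhere?** Yes. Section 9.3 requires documented consent before registration and before any study measure. Pregnancy has no matching limit.

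**The case against.** The strongest reply is that the eligibility rules already close the gap. A pregnant woman may not enter the trial, entry is decided at Visit 1, and the sentence says that pregnancy will already have been excluded. On that reading it names the source on which the study team relies at enrolment. The amendment history, used here only as evidence of intent, points the same way: it presents exclusion before radiotherapy as implying exclusion before xenon MRI. This stands as an account of what the authors meant. It does not close the gap, because that implication fails for the baseline scan and no readable sentence requires the Oncology result by Visit 1 or Visit 2.

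A reader might go further and infer that the check is scheduled for the start of radiotherapy, and so after the first xenon dose. The documents do not support that. The wording sets a latest time, not a date; the check may already be done by Visit 1, and no section places it after Visit 2.

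Other exclusions, such as severe renal impairment or a recent seizure, have no dated verification step either. That is true, and it argues against a general demand for more detail. Pregnancy differs because the plan does state a mechanism and a deadline, and the deadline is attached to an event later than the first dose.

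Section 9.10 lets the investigator discontinue a participant for pregnancy, or for ineligibility overlooked at screening. That is a real safeguard, but it acts after the event.

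Finally, the flow charts of section 7.2, the appendices and the case report form cannot be seen. A visit-level check or an eligibility tick-box may already exist there.

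**Conclusion.** The point holds in a limited form. The stated deadline does not by itself guarantee that pregnancy has been excluded before the first xenon dose and other study imaging at Visit 2. It does guarantee a check before Visits 3 to 5. This is a minor participant-safety improvement, with no effect on endpoints, analysis or sample size.

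The risk cannot be sized from the documents. They give neither the number of women of child-bearing age expected among the 30 participants nor the interval between Visit 2 and the first fraction. Counting Visit 2 breath holds would not help: the count describes dosing rather than the chance of an undetected pregnancy, and section 9.5 allows a return session, so it is not fixed.

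A reader might also infer that xenon is known to be harmful in pregnancy. The readable documents state no such harm, and none is claimed here.

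The conclusion assumes that the unavailable pages and the case report form contain no earlier check. If they do, only the wording of the three sections needs to be aligned with them.

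**What to change.** In section 9.3, and in the matching sentences of sections 7.1 and 10.1, change the deadline. Suggested wording: *The study team will confirm and record that pregnancy has been excluded in every female participant of child-bearing age before the first study imaging at Visit 2.* Add a field to the eligibility form if there is not one already. The choice of test stays with Oncology and the investigators, and the check can remain part of routine care.

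The cost is one reworded sentence in three places and, at most, one form field. For some women the routine check will have to be brought forward to fall before Visit 2. Where Oncology already has the result by Visit 1, the only added work is to confirm and record it.
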